**PACT-Q2**  
**(Perception AntiCoagulant Treatment Questionnaire)**

- The purpose of this questionnaire is to understand your expectations and to assess your satisfaction with your anticoagulant treatment (treatment that stops the blood from clotting).
- Throughout the questionnaire, the term “taking” refers to how you take your anticoagulant treatment (either by pill or injection).
- Please read each question carefully, answering as openly as you can and without help from anyone. There are no wrong answers.
- All of the information you provide will be kept confidential.
- This questionnaire will take about **10 minutes** to complete.

**Convenience**

Please answer the following questions to help us understand how convenient it is to take your treatment.

Please check one box per line.

B1 - How difficult is it to take your anticoagulant treatment (i.e., pills or injections, number of pills or injections, frequency of intake ...)?

 1	 2	 3	 4	 5
Not at all	A little	Moderately	A lot	Extremely

B2 - How bothered are you by taking your anticoagulant treatment?

 1	 2	 3	 4	 5
Not at all	A little	Moderately	A lot	Extremely

B3 - Some anticoagulant treatments may need dose adjustments; how difficult is this for you?

 1	 2	 3	 4	 5
Not at all	A little	Moderately	A lot	Extremely

B4 - Certain medications CANNOT be taken with anticoagulant treatments; how difficult is this for you?

 1	 2	 3	 4	 5
Not at all	A little	Moderately	A lot	Extremely

B5 - It is recommended that certain foods be avoided while taking an anticoagulant treatment; how difficult is this for you?

 1	 2	 3	 4	 5
Not at all	A little	Moderately	A lot	Extremely

B6 - How difficult is it for you to take your anticoagulant treatment when you are away from home?

 1	 2	 3	 4	 5
Not at all	A little	Moderately	A lot	Extremely

B7 - How difficult is it for you to plan your time around your anticoagulant treatment (i.e., appointments with nurses, doctors or labs...)?

 1	 2	 3	 4	 5
Not at all	A little	Moderately	A lot	Extremely

B8 - How bothered are you by the medical follow-up required with your anticoagulant treatment?

 1	 2	 3	 4	 5
Not at all	A little	Moderately	A lot	Extremely

B9 - How difficult is it for you to take your anticoagulant treatment as directed on a regular basis?

 1	 2	 3	 4	 5
Not at all	A little	Moderately	A lot	Extremely

B10 - Do you feel more dependent on others (i.e partner, family, nurse...) because of your anticoagulant treatment?

 1	 2	 3	 4	 5
Not at all	A little	Moderately	A lot	Extremely

B11 - How worried are you about having to interrupt or stop your anticoagulant treatment?

 1	 2	 3	 4	 5
Not at all	A little	Moderately	A lot	Extremely

**REVIEW COPY**  
**Do not use without permission**

**Burden of Disease and Treatment**

Please answer the following questions to help us understand how your disease and its treatment affect you.

**Please check one box per line.**

C1 - Because of potential side effects (i.e., minor bruises, bleeding...), do you limit your usual activities (i.e., work, leisure, social, or physical activities...)?

 1	 2	 3	 4	 5
Not at all	A little	Moderately	A lot	Extremely

C2 - How much physical discomfort do you have due to bruises or pain?

 1	 2	 3	 4	 5
None	A little	Moderate	A lot	Extreme

**Anticoagulant Treatment Satisfaction**

Please answer the following questions to help us understand how satisfied you are with your treatment.

Please check one box per line.

D1 - How reassured do you feel by your anticoagulant treatment?

 1	 2	 3	 4	 5
Not at all	A little	Somewhat	Very	Completely

D2 - Do you feel that your anticoagulant treatment has decreased your symptoms (i.e., leg pain or swelling, palpitations, shortness of breath, or chest pain...)?

 1	 2	 3	 4	 5
Not at all	A little	Moderately	A lot	Completely

D3 - How did your experience with side effects such as minor bruises or bleeding (i.e., while shaving, cooking, after small cuts...) compare to what you expected?

 1	 2	 3	 4	 5
It is much worse than what I expected	It is worse than what I expected	It is exactly what I expected	It is better than what I expected	It is much better than what I expected

D4 - Regarding the follow-up of your disease and anticoagulant treatment, how satisfied are you with your level of independence?

 1	 2	 3	 4	 5
Extremely dissatisfied	Dissatisfied	Neither satisfied nor dissatisfied	Satisfied	Extremely satisfied

D5 - How satisfied are you with the methods (i.e., appointments with nurses, doctors, labs...) used to ensure the follow-up of your disease and anticoagulant treatment?

 1	 2	 3	 4	 5
Extremely dissatisfied	Dissatisfied	Neither satisfied nor dissatisfied	Satisfied	Extremely satisfied

D6 - How satisfied are you with the form of your anticoagulant treatment (oral pill / injection)?

 1	 2	 3	 4	 5
Extremely dissatisfied	Dissatisfied	Neither satisfied nor dissatisfied	Satisfied	Extremely satisfied

D7 - Overall, how satisfied are you with your anticoagulant treatment?

 1	 2	 3	 4	 5
Extremely dissatisfied	Dissatisfied	Neither satisfied nor dissatisfied	Satisfied	Extremely satisfied

**Please make sure you answered all questions.**

**Thank you for your time.**

2. LIST OF ABBREVIATIONS

Term	Definition / description
ADR	Adverse drug reaction
AE	Adverse event
BI	Boehringer Ingelheim
b.i.d.	bis in die (two times a day)
BMI	Body Mass Index
CI	Confidence interval
DVT	Deep venous thrombosis
ECG	Electrocardiogram
eCRF	Electronic case report form
EDC	Electronic data capture
EoT	End-of-text
ICH	International Conference on Harmonisation
INR	International normalized ratio
IPV	Important protocol violation
ISPE	International Society for Pharmaceutical Engineering
LMWH	Low molecular weight heparin
LOS	Length of stay
MedDRA	Medical Dictionary for Regulatory Activities
mg	Milligram
MQRM	Medical quality review meeting
NIS	Non-interventional study
NOAC	Non-vitamin K anticoagulant
PACT-Q [®]	Perception of Anticoagulant Treatment Questionnaire
PE	Pulmonary embolism
PV	Protocol violation
Q1	Lower quartile
Q3	Upper quartile
SD	Standard deviation
SEAP	Statistical and epidemiological analysis plan
UFH	Unfractionated heparin

Term	Definition / description
VKA	Vitamin K antagonist
VTE	Venous thromboembolism
WHO	World Health Organization

3. INTRODUCTION

As per ICH E9 [1] and the ISPE Guidelines of Good Pharmacoepidemiology Practice [2], the purpose of this document is to provide a more technical and detailed elaboration of the principal features of the analysis described in the protocol, and to include detailed procedures for executing the statistical analysis of the data. This document describes the final analysis at the end of study for Objective 1 as well as the interim analyses which will be performed at the end of each of the first two enrolment periods for Objective 1.

This SEAP assumes familiarity with the non-interventional study (NIS) protocol including Protocol Amendments. In particular, the SEAP is based on the planned analysis specification as written in the NIS protocol Section 9 “Research Methods”. Therefore, SEAP readers may consult the NIS protocol for more background information on the study, e.g., on study objectives, study design and population, treatments, definition of measurements and variables, planning of sample size.

SAS[®] Version 9.3 or higher will be used for all analyses.

4. CHANGES IN THE PLANNED ANALYSIS OF THE STUDY

It was originally planned in the protocol that approximately 2,000 patients would be enrolled into Objective 1 per year over three years for a total of 6,000 patients, and that the study would include an analysis of the patients from each enrollment year through two interim analyses. Subsequently, a decision was made by the study team to continue Objective 1 enrollment without pausing between years until the total target of 6,000 patients is reached. As a result, it is projected that the enrollment for Objective 1 will be completed in less than two years. In light of this change, it is now planned that only one interim analysis will be performed with data from approximately the first 3,000 patients.

5. OUTCOMES

Objective 1 of the RE-COVERY study is designed to characterize the deep vein thrombosis (DVT)/pulmonary embolism (PE) patient population including the initial acute event phase. All patients with a DVT and/or PE will be enrolled for cross-sectional characterization of the venous thromboembolism (VTE) patient population and descriptions of current treatment patterns, and stratified by geographical location.

The following research questions will be investigated:

- With the approval of dabigatran etexilate and other non-vitamin K anticoagulants (NOACs), what treatments are being administered for acute VTE in routine clinical practice in the different regions of the world?
- When presenting with an acute VTE event, what factors influence the choice of treatment for the event?

5.1 MAIN OUTCOMES

The following primary outcome measures will be analyzed on data that are collected at the time of the acute VTE event:

- Demographic information (age and gender)
- VTE event information (event type and treatment for event)

6. GENERAL ANALYSIS DEFINITIONS

6.1 EXPOSURE

For Objective 1, VTE treatment information will be collected at two time points, baseline and hospital discharge/14 days after baseline, due to the requirement of heparin pre-treatment for some of the studied oral anticoagulants.

On the eCRF page, five oral anticoagulants (vitamin K antagonist, dabigatran, edoxaban, rivaroxaban, and apixaban) are included as pre-specified options, together with three types of heparin pre-treatment (low molecular weight heparin, unfractionated heparin, and fondaparinux) and two types of non-oral therapies (systemic thrombolytic therapy and catheter directed thrombolytic therapy). Patients will be assigned to one of the five oral anticoagulant groups or an additional “Other” group (defined as patients with no oral anticoagulant prescribed), based on the following rules.

Table 6.1: 1 Oral anticoagulant treatment assignment

Treatment at baseline	Treatment at hospital discharge/14 days	Treatment assignment
Vitamin K antagonist ¹	Same as baseline	Vitamin K antagonist
Dabigatran ¹		Dabigatran
Edoxaban ¹		Edoxaban
Rivaroxaban		Rivaroxaban
Apixaban		Apixaban
Heparin pre-treatment without any oral anticoagulant and without non-oral/other therapy	Vitamin K antagonist	Vitamin K antagonist
	Dabigatran	Dabigatran
	Edoxaban	Edoxaban
	Rivaroxaban	Rivaroxaban
	Apixaban	Apixaban
Any of the following without oral anticoagulant: Systemic thrombolytic therapy Catheter directed thrombolytic Other	Same as baseline	Other

¹ Although heparin pre-treatment is required for vitamin K antagonist, dabigatran and edoxaban, these scenarios are included to account for the possibility that these treatments were entered on the baseline eCRF page by the sites due to the retrospective enrollment of patients.

In the event that patients with other combinations of treatment information at baseline and hospital discharge/14 days, such as those listed below, are identified, their treatment assignment should be discussed and determined on a case-by-case basis by the study team during the periodical medical quality review meetings (MQRMs). In the event that a decision

cannot be made due to contradictory information, these inconsistencies should be queried and resolved by the sites.

- More than one oral anticoagulant was entered at a single time point
- A different oral anticoagulant was entered at hospital discharge/14 days than at baseline
- Both an oral anticoagulant and a non-oral/other therapy were entered at a single time point
- Different non-oral therapies were entered at hospital discharge/14 days than at baseline

6.2 IMPORTANT PROTOCOL VIOLATIONS

Patients with important protocol violations (IPVs) will be documented. The list of all protocol violations (or deviations) and their handling rules are documented in detail in the separate document Protocol Deviation Specification.

Additional IPVs may be defined during the course of the study, based on assessments at the MQRMs; if the list of IPVs needs to be enlarged, it will be documented in the report planning meeting minutes before database lock.

6.3 PATIENT SETS ANALYSED

The planned analysis for Objective 1 will be based on all eligible patients (i.e. all patients who fulfil all inclusion criteria and no exclusion criteria).

6.5 POOLING OF CENTERS

Centre will not be used as a variable in any analysis; therefore this section is not relevant.

6.6 HANDLING OF MISSING DATA AND OUTLIERS

For Objective 1, the presence of missing data is expected to be low, since the variables are expected to be collected in routine clinical practice and should therefore be available in the patient's medical record. As a result, any missing data will be treated as missing and no imputation will be performed.

The amount of missing data will be reported in the descriptive summary tables (i.e. a 'Missing' category will be displayed for variables with missing data).

Depending on the amount of missing data (e.g., >10% for a key variable), sensitivity analysis may be performed, where the distribution of other variables (age, sex, and other patient characteristics) will be compared between patients with and without missing data for each variable, and reported.

6.7 BASELINE, TIME WINDOWS AND CALCULATED VISITS

The planned analysis for Objective 1 is cross-sectional in nature. However, in addition to the data collected at the baseline visit, additional data at hospital discharge or 14 days after the baseline visit (whichever later) will be collected and included in the analysis. This is because the treatment with some NOACs (e.g. dabigatran and edoxaban) requires 5 to 10 days of pre-treatment with parenteral therapy.

7. PLANNED ANALYSIS

Summary statistics for continuous variables will include the number of observations (N), mean, standard deviation (SD), minimum, Q1 (25th percentile), median, Q3 (75th percentile), and maximum; tabulations of categorical variables will present all possible categories and will display the number of observations per category as well as percentages. The default precision for percentages should be one decimal place, unless otherwise specified. In general, percentages will be based on all patients in the analysis population, whether they have missing data or not. A category 'Missing' will be displayed whenever at least one patient falls within this category. For variables based on nested questions (i.e. questions which ask for more detailed information only within the subgroup of patients with a specific value for another higher level question), percentages will be based on the patients with the corresponding value for the higher level question.

Individual patient listings will be created, which generally will be sorted by anticoagulation treatment at baseline, region, country, center number and subject number, and be based on the analysis population used for the corresponding table.

7.1 DEMOGRAPHIC AND OTHER BASELINE CHARACTERISTICS

Analysis of demographic and other baseline characteristics is defined as a main analysis for Objective 1. Details regarding the main analysis can be found in Section 7.6.

7.2 CONCOMITANT DISEASES AND MEDICATION

Analysis of baseline concomitant diseases and medication is defined as a main analysis for Objective 1. Details regarding the main analysis can be found in Section 7.6.

7.3 TREATMENT ADHERENCE

Not applicable for Objective 1 of this study.

7.4 METHODS ADDRESSING BIAS

See study protocol.

7.5 METHODS ADDRESSING CONFOUNDING/EFFECT MEASURE MODIFICATION

Not applicable for Objective 1 of this study.

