#### 9.3.1.1 Baseline visit data points

The Flowchart (Table [9.3.1:1](#) and Table [9.3.1:2](#)) outlines all of the data points to be collected. No study procedures or data recorded in the EDC system should be performed unless the patient has consented to participate in the study or a waiver has been obtained in accordance with local regulations. As in any observational study, patients will be managed according to local clinical practice. The choice of treatment is solely at the discretion of the participating physicians. This means there are no additional medical or procedural risks to patients by

participating in this study. No additional medical procedures are required, over and above those that the patient would receive if not enrolled.

- Review of in- and exclusion criteria
- Demographic data will include year of birth, gender, race (as allowed by local regulations), insurance status
- Height, weight, blood pressure, and heart rate
- Available laboratory data (e.g., serum creatinine, hemoglobin, and INR)
- Information regarding the index VTE event including:
  - date of diagnosis,
  - risk factors for VTE (i.e., if the VTE was provoked or unprovoked),
  - clinical signs and symptoms and
  - the following variables based on objective testing (e.g. Venous compression ultrasonography, venography for DVT CT, MRI and any other examination that is deemed relevant per routine clinical practice for DVT diagnosis or ventilation-perfusion (V-Q) lung scan, pulmonary angiography or spiral (helical) computed tomography scan for PE):
    - Date of diagnostic testing
    - Location, extent and severity of venous thrombus
    - Impression or findings
- Treatment for VTE should include all treatment details including specific therapies provided for the event, start date(s) and stop dates (if applicable), dosage, planned treatment duration, and rationale for treatment choice.
- Medical history including current concomitant diseases, history of previous VTE (if any) risk factors (i.e., if the VTE was provoked or unprovoked) for VTE re-occurrence and risk factors for bleeding.
- Concomitant therapies that are being currently used by the patient including the name of the therapy and indication.

9.3.1.2 Hospital discharge or at 14 days after diagnosis of VTE event (whichever occurs later)

For [Objective 1](#), the additional data points will include:

- Any changes to the treatment for the VTE event
- Date of hospital discharge, if patient was admitted to hospital

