## **9.5 STUDY SIZE**

For [Objective 1](#):

It is planned that a total of approximately 6000 patients will be enrolled. This is not based on formal sample size calculations as there are no hypotheses to be tested. If eligible, patients included in the cross-sectional assessment (Objective 1) who are treated with dabigatran etexilate and a similar number of those treated with VKA will be followed ([Objective 2](#)).

Baseline demographics and characteristics of the patient population will be described by estimates and confidence intervals (CI) overall and by relevant categories as specified in Section [9.7](#) and the statistical and epidemiological analysis plan SEAP. Categorical attributes will be estimated with the precision (i.e., width of descriptive 95% CI) described in Table [9.5:1](#), according to sample size and prevalence of the attribute.

Table 9.5:1 Width of 95% CI by sample size and prevalence of attribute

Prevalence of attribute	Sample size (overall or per subgroup)					
	500	1000	2000	3000	4000	6000
5% Expected n	25	50	100	150	200	300
95% CI width	4.03	2.81	1.96	1.59	1.38	1.12
10% Expected n	50	100	200	300	400	600
95% CI width	5.46	3.82	2.68	2.18	1.88	1.54
20% Expected n	100	200	400	600	800	1200
95% CI width	7.20	5.05	3.55	2.90	2.50	2.04
30% Expected n	150	300	600	900	1200	1800
95% CI width	8.21	5.77	4.06	3.28	2.86	2.34
40% Expected n	200	400	800	1200	1600	2400
95% CI width	8.77	6.17	4.34	3.54	3.06	2.49
50% Expected n	250	500	1000	1500	2000	3000
95% CI width	8.94	6.29	4.43	3.61	3.12	2.54

\* Calculations are based on the Clopper-Pearson method.

For example, if an attribute has a prevalence of 40% in the population of acute VTE patients, with a sample size of 2000 patients, this proportion can be estimated with a precision of 4.34% (i.e. width of 95% CI). Furthermore, in a subgroup that consists of 1000 patients, this same proportion can be estimated with a precision of 6.17%.

For [Objective 2](#):

Baseline data will be summarized descriptively for eligible patients using a similar approach as described above for Objective 1. Categorical attributes will be estimated with the precision described in Table 9.5:1. For example, a sample size of 2000 patients allows a population attribute with a 30% prevalence to be estimated with a precision of 4.06%.

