#### **9.7.2.1 Main analyses**

For Objective 1:

Baseline patient demographics and disease characteristics, including information regarding the index VTE event, medical history, concomitant therapies, and laboratory data as specified in [Section 9.3.1](#), will be summarized descriptively for all eligible patients overall and by anticoagulation treatment at baseline. The analysis will be repeated by region and by additional relevant patient attributes.

Patterns of anticoagulation treatment at baseline will be described overall, by region, and by additional relevant patient attributes.

For Objective 2:

Patient demographics and disease characteristics at baseline as described above for Objective 1 will be summarized descriptively for all eligible patients by their initial anticoagulation treatment (i.e. dabigatran etexilate or VKA). This analysis will be repeated by region and by additional relevant patient attributes.

Given the observational nature of this study, patients in the dabigatran etexilate and VKA groups may differ with regard to important baseline demographics and disease characteristics. When the target sample size is reached, propensity scores that estimate the probabilities that patients would be initiated on dabigatran etexilate will be calculated using a logistic regression model that considers variables that are risk factors for the occurrence of VTE or bleeding events or affect the choice of anticoagulation treatment (details of the model will be provided in the SEAP). Overlap of propensity scores between the dabigatran etexilate and VKA groups will be examined to assess the comparability of the two patient populations, and to estimate the loss of patients from the comparative analysis if trimming or matching is to be performed.

The primary safety and effectiveness outcomes will be analyzed for dabigatran etexilate patients in comparison to VKA patients using Cox proportional hazards models. Confounding will be controlled for using appropriate methods, including adjustment of covariates in the Cox regression model, trimming of extreme observations, and/or propensity score matching, based on the evaluation of the comparability of dabigatran etexilate and VKA patients (i.e. overlap of propensity scores) as described above. Details of the analytical methods and the selection rules of the appropriate analysis strategy will be provided in the SEAP.

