7.6 MAIN ANALYSES

Descriptive summaries of baseline patient characteristics as specified in [Section 5](#) will be created for the overall population and by anticoagulation treatment. These analyses will be repeated by the subgroup variables defined in [Section 6.4](#).

Descriptive summaries of anticoagulation treatment patterns, including the observed combinations of treatment at baseline and at hospital discharge/14 days as described in [Table](#)

[6.1: 1](#), will be created for the overall population. These analyses will be repeated by the subgroup variables defined in [Section 6.4](#).

As an exploratory analysis, baseline characteristics of the dabigatran patients will be summarized separately by the following dose groups, if the subgroups consist of at least 200 patients:

- 150 mg b.i.d.
- 110 mg b.i.d.
- 75 mg b.i.d.
- Other doses

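### Objective 1 asks which factors influence treatment choice, but its visible SAP plans descriptive tables by drug that cannot separate correlated characteristics

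*SAP*

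**What the plan says.** Protocol section 8 and section 5 of the Objective 1 SAP pose the same question: "When presenting with an acute VTE event, what factors influence the choice of treatment for the event". The Objective 1 SAP lists two research questions, and this is the second.

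For the analysis, section 7.6 of that SAP begins "Descriptive summaries of baseline patient characteristics as specified in" section 5 and says that these "will be created for the overall population and by anticoagulation treatment". It adds "These analyses will be repeated by the subgroup variables defined in" section 6.4. Treatment patterns are tabulated in the same way. Protocol 9.7.2.1 is consistent with this: "The analysis will be repeated by region and by additional relevant patient attributes". Under methods addressing confounding and effect measure modification, SAP 7.5 says "Not applicable for Objective 1 of this study".

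On the data, protocol 9.3.1.1 asks sites to record the treatment details, including "planned treatment duration, and rationale for treatment choice". On size, protocol 9.5 says "It is planned that a total of approximately 6000 patients will be enrolled". It adds that no hypothesis is tested, and it describes precision by confidence interval width in Table 9.5:1.

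**The concern.** A question about what influences choice has several candidate answers that tend to occur together: age, renal function, cancer, type of index event, previous VTE, insurance, region. A table of each characteristic by drug shows how the treated groups differ. It does not show whether a difference in one characteristic remains once the others are held fixed. Repeating the table within subgroups fixes one further variable at a time and leaves the rest free.

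With about 6,000 patients the differences will look precise. Readers who have been promised an answer about influence may take each clear difference as a separate determinant of prescribing. The same tables may also be cited informally when preferential prescribing, which protocol 9.9 discusses under channelling bias, is considered for Objective 2.

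**Working it through.** **1. Does any visible analysis address the question with adjustment?**

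| Place | What it provides |
|---|---|
| Objective 1 SAP 5 | Poses the question of influence on choice |
| Objective 1 SAP 7.6 | Descriptive summaries by drug and subgroup |
| Objective 1 SAP 7.5 | Confounding methods declared not applicable |
| Objective 2 SAP 5 | Refers the question back to the Objective 1 SAP |
| Objective 2 SAP 7 and 7.6 | Logistic propensity model, dabigatran against VKA only, used for trimming and weighting |

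The propensity model does not fill the gap. It leaves out patients on edoxaban, rivaroxaban, apixaban or no oral anticoagulant, all of whom have a group in Table 6.1:1 of the Objective 1 SAP. Its covariates are chosen for their link with the outcomes. Insurance status, which protocol 9.3.1.1 collects, is not in Table 7.6:1, although protocol 9.9 notes that dabigatran may or may not be reimbursed.

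**2. The plan's own precision figure.** Table 9.5:1 uses the Clopper-Pearson interval: lower limit = Beta quantile(0.025; x, n − x + 1), upper limit = Beta quantile(0.975; x + 1, n − x). For 40% of 2,000, x = 800 and the width is 4.34 points, as printed. Of the 36 cells, 35 reproduce within 0.01 point. The other (30%, n = 3,000) is printed as 3.28 and computes to 3.31, which does not matter here.

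**3. How far can a marginal contrast differ from an adjusted one?** All inputs in this step are assumptions, not document figures. Characteristic A is present in 25% of patients. Characteristic B is present in 50% of those with A and 10% of those without. Choice of a given drug depends on B only: probability 0.50 without B, odds ratio 0.5 with B. With B the odds are 0.5, so the probability is 0.5/1.5 = 0.333.

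- P(drug | A) = 0.5 × 0.333 + 0.5 × 0.5 = 0.417
- P(drug | not A) = 0.1 × 0.333 + 0.9 × 0.5 = 0.483
- Crude odds ratio for A = (0.417/0.583) / (0.483/0.517) = 0.76
- Share with A among those given the drug = 0.25 × 0.417 / (0.25 × 0.417 + 0.75 × 0.483) = 22.3%
- Share with A among the others = 0.25 × 0.583 / (0.25 × 0.583 + 0.75 × 0.517) = 27.3%
- Odds ratio for A with B held fixed = 1.00 by construction

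At n = 6,000 the two groups hold about 2,800 and 3,200 patients. Table 9.5:1 gives widths near 3 points for such shares at 3,000 patients, so a 5-point gap would look well established. In 300 simulated data sets of 6,000, the mean crude odds ratio was 0.76 (p < 0.05 in 99.7%) and the mean adjusted odds ratio 1.00 (p < 0.05 in 4.7%).

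**4. Range.** With P(B | A) from 30% to 60% and the odds ratio for B from 0.7 to 0.33, the crude odds ratio for A runs from 0.93 to 0.59. If A and B are uncorrelated, or B has no bearing on choice, it is 1.00.

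Step 3 shows that the two quantities differ. It does not show that the crude one is wrong: if A brings about B, the crude odds ratio is the total association of A with choice.

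**The case against.** The strongest reply is that Objective 1 is a cross-sectional description. Protocol 9.5 states that it tests no hypotheses, and 9.7.1 calls the analyses descriptive. For the primary outcome measures (age, gender, event type, treatment), confounding methods are indeed not needed. This stands for those outcomes. It does not cover the second research question, and 9.7.1 itself allows statistical models for exploratory use, so a regression would fit the protocol.

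The public text is also incomplete. The Objective 1 SAP refers to a section 6.4 that is not shown, its numbering passes from 7.6 to 7.8, and its contents list gives section 5 about four pages, of which little is visible. Protocol 9.7.2.2 is missing too. A further analysis of treatment choice could sit there. This stands, and it limits the point to the visible plan.

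The subgroup repeats go beyond region, since protocol 9.7.2.1 adds other patient attributes. That is real stratification, though limited.

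A reader might infer that the recorded reasons for choice go unused. The documents do not establish that. Protocol 9.3.1.1 places them within treatment for VTE, treatment for the event is a primary Objective 1 measure, and the detailed variable list is not shown.

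Finally, mutual adjustment has its own problems. If age lowers renal function and renal function guides prescribing, adjusting for renal function removes part of what age does. Section 7.9.2 of the Objective 1 SAP derives creatinine clearance by Cockcroft-Gault, which already contains age and weight. An adjusted coefficient is therefore no more a causal driver than a crude one.

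**Conclusion.** The mismatch holds in a limited form. The question is worded as influence, the visible analysis is descriptive by drug and subgroup, and 7.5 rules confounding methods out. Marginal tables cannot separate correlated characteristics, so the result may be over-read. The possible size depends on assumptions: none if the characteristics are uncorrelated, a crude odds ratio of 0.93 to 0.59 against an adjusted 1.00 over the range tried. No sample size or precision figure in the documents is affected.

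Three stronger readings are not supported:

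- A reader might infer that the sponsor will report table differences as drivers of choice. No passage says so; it is a risk of interpretation.
- A reader might infer that marginal differences are spurious. They are valid descriptions, and some may be total effects.
- A reader might infer that the Objective 2 comparison is damaged. It has its own propensity model, overlap weights and balance checks, none of which uses the Objective 1 tables.

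This is a worthwhile, inexpensive improvement that lets Objective 1 address its own question. It does not invalidate the planned description.

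**What to change.** Replace the entry in section 7.5 of the Objective 1 SAP with a prespecified exploratory analysis:

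- **Model:** multinomial logistic regression of treatment group, with VKA as reference and dabigatran, other NOAC and no oral anticoagulant as the other levels.
- **Covariates:** age, sex, renal function, BMI, event type, provoked status, prior VTE, cancer, prior bleeding, antiplatelet use and insurance status, with region as a fixed effect.
- **Site:** no site term, because section 6.5 says that centre is not used in any analysis. If site-clustered standard errors or a random intercept are wanted, amend 6.5 first.
- **Missing data:** state a rule, since section 6.6 excludes imputation. Either report a complete-case analysis with the number excluded, or amend 6.6. Renal function is the likely weak spot, because protocol Table 9.3.1:1 collects laboratory data only if available.
- **Reporting:** adjusted odds ratios with 95% confidence intervals beside the tables, described as mutually adjusted associations and not as causes, with a note that Cockcroft-Gault clearance contains age and weight.
- **Reasons for choice:** tabulate the recorded rationale by drug and region, if the non-public sections do not already do so.

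If no model is added, reword the question as a description of patient characteristics by treatment and drop the language of influence.

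The cost is a SAP amendment, one model and one table, on data the protocol already collects. The downside is a set of coefficients that need careful interpretation.
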